### 6.3. MISSING DATA

Several different methods to handle the missing data in efficacy assessments will be used.

## Statistical Analysis Plan

- For the primary analysis of spirometry and selected efficacy endpoints, likelihood-based modeling approach will be used to handle incomplete data. For this purpose, Mixed Model for Repeated Measures (MMRM) will be applied (see [Section 8.1.](#))
- Sensitivity analysis for spirometry and selected explorative efficacy endpoints will be conducted using the Multiple Imputation (MI) approach, i.e. by replacing each missing value with a set of plausible values that represent the uncertainty about the right value to impute, see [Section 9.1.](#)
- For the binary explorative efficacy endpoints, sensitivity analyses will be conducted using worst case imputation, where visits with missing data are counted as non-resolved (primary method), see [Section 8.1.](#)
- For AEs, the overall incidence of TEAEs, normalized for duration of exposure will be calculated to account for the shorter follow-up time in patients who discontinue the study prematurely, see [Section 9.4.](#)

The Safety and ITT population will be used for the analysis of the primary and secondary endpoints. This population includes all patients enrolled to study CVT-301-004E who received at least 1 dose of inhaled CVT-301, regardless of whether they have post-baseline data or not for the variable in question. The patients with no post-baseline data will not contribute to the analyses performed with the MMRM approach, but they do contribute to the sensitivity analyses using the MI approach. Due to this, no additional population, like a modified ITT population including only the patients with post-baseline will be defined.

Safety data (other than the primary endpoint) will not be subjected to any imputation and will be summarized on an observed case basis.

### 6.4. VISIT WINDOWS

The visits recorded in database will be used for all analyses. There is no plan to re-assign visits based on actual visit dates.

For the patients who discontinue the study prematurely, a set of assessments is scheduled to be performed at the ET visit (PDQ-39, PHQ-9, PGI-C, UPDRS Part 2, UPDRS Part 4, S&E ADL score and safety assessments). The following rules will be used to analyze the data collected at the ET visit:

- For the PDQ-39, PHQ-9, PGI-C, UPDRS Part 2, UPDRS Part 4 and S&E ADL score, the data from the ET visit will be re-assigned to TV6 in case there is no TV6 assessment.

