### 4.3. SAFETY ENDPOINTS

The following endpoints related to the secondary objectives will be calculated.

- Standard safety endpoints; for definitions see Section 9 of this SAP
  - Adverse Event (AE) reports
  - Physical examination
  - Standard and orthostatic vital signs (BP, HR and RR)
  - Clinical laboratory tests (hematology, clinical chemistry, and additional laboratory parameters)
  - 12-lead ECGs (HR, PR, QRS, QT, QT interval corrected using Bazett's formula [QTcB] and QT interval corrected using Fridericia's formula [QTcF])
  - Parkinson's Disease Impulsive-Compulsive Disorders Questionnaire (QUIP)
  - Epworth Sleepiness Scale
  - Columbia-Suicide Severity Rating Scale (C-SSRS)
- Occurrence and severity of examiner-rated dyskinesia following treatment of patients experiencing an OFF episode in the clinic. The occurrence will be based on the examiner's subjective assessment and no further derivation will be performed. Among the patients with reported dyskinesia, the severity will be classified as mild, moderate, severe or missing based on the examiner's subjective assessment and no further derivation will be performed. Only observed cases will be used for this endpoint and the visits with missing data will not be included in the analysis.
- Change from TV1 (baseline) in the UPDRS Part 4 sum scores of dyskinesias (UPDRS items 32-35) and wearing-off (UPDRS items 36-39). The dyskinesia score will be calculated as the sum of the individual items 32-35 and the wearing-off score as sum of 36-39. Missing individual items will not be imputed and the sum score will be missing in case of 1 or more missing items.
- Carbon Monoxide Diffusion Capacity (DLCO) assessed over a 12 month period. Variables will include the absolute DLCO values and DLCO expressed as % of predicted value.

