## Statistical Analysis Plan

- In case there are PD diary assessments performed during the three days before the ET visit, these assessments will be re-assigned to the first visit at which the PD diary assessments were scheduled but are missing due to the premature withdrawal.
- The safety assessment assessments performed at the ET visit will be re-assigned to the first time point at which the corresponding safety assessments were scheduled but are missing due to the premature withdrawal.
- Any other data collected at the ET visit will not be used.

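### SAP 6.4 analyses early-termination scores on six scales as TV6 (Week 52) values whatever the withdrawal date, while diary and safety data from the same visit go to the first missed visit

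*SAP*

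**What the plan says.** SAP 6.4 sets three rules for data collected at an ET visit.

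- For PDQ-39, PHQ-9, PGI-C, UPDRS Part 2, UPDRS Part 4 and S&E ADL, "the data from the ET visit will be re-assigned to TV6 in case there is no TV6 assessment".
- PD diary entries from the three days before the ET visit are "re-assigned to the first visit at which the PD diary assessments were scheduled but are missing due to the premature withdrawal".
- Safety assessments are "re-assigned to the first time point at which the corresponding safety assessments were scheduled but are missing due to the premature withdrawal".

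The section also states: "There is no plan to re-assign visits based on actual visit dates". Nothing else limits how far an ET value may be moved.

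Protocol 10.1.5 has withdrawing patients complete the TV6 assessments when they withdraw, and SAP 3.8 places TV6 at Week 52. SAP 8.1 analyses S&E ADL, UPDRS Part 2, PHQ-9 and PDQ-39 by ANCOVA and descriptive summaries on observed cases.

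UPDRS Part 4 is named in the TV6 rule. It is also a safety endpoint in SAP 4.3, is analysed in the safety section (SAP 9.12) with an MMRM like that for spirometry, and appears among the safety assessments in protocol 11.1.12.1. The introduction to the ET rules, however, lists "UPDRS Part 2, UPDRS Part 4, S&E ADL score and safety assessments", which sets UPDRS Part 4 apart from the safety assessments.

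The visit-pooling table in SAP Section 8 takes Months 6 to 12 for the CVT-301-004 active group from the 004E Month 3 to 9 visits. It uses neither the 004E Month 1 visit nor the 004E Month 12 visit for that group.

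**The concern.** Take a patient who withdraws at Week 6, after TV2. The Epworth score and the diary data from the ET visit are assigned to TV3 (Week 12). The PHQ-9 score from the same visit is assigned to TV6 (Week 52). The SAP gives no reason for the difference.

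Once relabelled, the PHQ-9 score counts as an observed TV6 case. The last-visit estimates for these scales then mix treatment durations from a few weeks to a year, and nothing in the planned tables tells the reader so. SAP 6.3 does not list this re-assignment among its methods for missing data.

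For UPDRS Part 4, on the TV6 reading, a mistimed value fills the TV6 cell of an MMRM that SAP 6.3 chose so that incomplete data would be handled by likelihood. For active rollovers the effect is different: their relabelled efficacy values land in a visit that the pooled analysis does not use, so they are lost.

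**Working it through.** **Inputs.** Planned enrolment is 390, with about 290 completers (SAP 3.5). TV2 to TV6 fall at Weeks 4, 12, 24, 36 and 52 (SAP 3.8). ET attendance, withdrawal timing and the rollover mix are not in the documents, so they are assumed below and shown as ranges.

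**The plan's own figure.** SAP 3.5 says the sample size has no formal statistical basis, so there is no power figure to reproduce. Implied non-completion is 1 − 290/390 = 25.6%. As a consistency check, 290/(1 − 0.25) = 387, close to 390.

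**Ceiling on ET values labelled TV6.** With E withdrawals attending an ET visit, the share is E/(290 + E).

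- All 100 attend: 100/390 = 25.6%
- 80 attend: 80/370 = 21.6%
- 60 attend: 60/350 = 17.1%
- 50 attend: 50/340 = 14.7%

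**How early these values are (all 100 attend).** If withdrawal is uniform over 52 weeks, 100 × 36/52 = 69.2 occur before Week 36. Under a constant hazard, h = −ln(290/390)/52, retention to Week 36 is exp(−36h) = 0.815 and 72.3 withdrawals occur before Week 36. ET values from before Week 36 are therefore 17.8% to 18.5% of the 390 TV6-labelled values; those from before Week 24 are 11.8% to 12.8%.

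**Pooled efficacy Month 12.** Let f be the fraction of the analysed patients who are CVT-301-004 active rollovers. Their Month 12 comes from the 004E Month 9 visit. With d = 0.256, equal dropout across groups and full ET attendance, the share is (1 − f)d / [(1 − f) + 0.815f].

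| f | Share of Month 12 that is ET data |
|---|---|
| 0 | 25.6% |
| 0.2 | 21.3% |
| 0.4 | 16.6% |
| 0.5 | 14.1% |
| 0.6 | 11.5% |

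At f = 0.5, about 50 of 100 ET values would fall in the unused visit.

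**After the change.** Under the first-missed-visit rule only withdrawals after TV5 stay at TV6.

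- Uniform: 100 − 69.2 = 30.8, and 30.8/320.8 = 9.6%
- Constant hazard: 100 − 72.3 = 27.7, and 27.7/317.7 = 8.7%

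**Effect on a TV6 mean or proportion (observed cases).** If all ET scores share one mean, the shift is the change in share times the withdrawal-minus-completer difference: 0.256 − 0.096 = 0.160 to 0.256 − 0.087 = 0.169. Each 10 units of difference would move the TV6 result by about 1.6 to 1.7 units.

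**Mistiming.** On nominal visit times the TV6 rule can move a value forward by almost 52 weeks. The first-missed-visit rule moves it by at most the widest gap between visits, 52 − 36 = 16 weeks.

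**The case against.** The rule is written openly in the SAP and follows the visit structure, since the protocol makes TV6 and the early withdrawal visit one visit. Mapping the withdrawal assessment to end of study is a recognisable convention. The first-missed-visit rule also mistimes data: a Week 5 score would be labelled Week 12. The affected endpoints are secondary or safety endpoints, PGI-C is descriptive, and SAP 8.1 plans no inferential comparison of dose groups for efficacy. Primary spirometry and diary OFF time are outside the TV6 rule. These points stand, and they limit the consequence. They do not justify treating a Week 6 score as an observed Week 52 score when the same section already has a rule with a much smaller error.

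Four stronger readings are tempting, and the documents do not support them.

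- A reader might infer that a quarter of all Month 12 values will be early data. The 25.6% is a planning ceiling for TV6-labelled values. It requires every non-completer to attend, although protocol 8.3 lists death and loss to follow-up among the withdrawal reasons. It also ignores Section 8, and some of the values come from withdrawals after TV5.
- A reader might infer that two rules flatly contradict each other for UPDRS Part 4. SAP 6.4 names the scale in the TV6 rule and lists it apart from safety assessments, which favours TV6. The safety classification elsewhere makes this an ambiguity.
- A reader might call the rule concealed carry-forward. It is stated in the SAP; what is missing is a label on the results.
- A reader might multiply 25.6% by an assumed PGI-C gap and call that the bias. That ignores the ET values that stay at TV6 under any next-visit rule. It also ignores the title of Table 14.2.3.1, which refers to worst-case imputation.

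**Conclusion.** The concern holds as a timing and labelling defect in secondary and safety endpoints. ET values of six scales are analysed as Week 52 values with no limit on withdrawal date, against the rule the same section uses for other data from the same visit. At most 25.6% of TV6-labelled values are affected, or 14.7% to 21.6% with 50% to 80% ET attendance. For pooled efficacy Month 12 the share is lower to the extent that active rollovers contribute, and their ET values are lost to that analysis.

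The observed-case change from correcting the rule is about 0.16 to 0.17 times the withdrawal-completer difference. That assumes full ET attendance, uniform or constant-hazard withdrawal, and the SAP's 52-week schedule. The protocol puts TV6 at 56 or 60 weeks, which would leave somewhat more withdrawals in the last interval. The documents give no value for the difference, so the direction and absolute size of any bias cannot be stated. For UPDRS Part 4 the SAP needs one stated rule; on the TV6 reading, a mistimed value enters its MMRM.

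**What to change.** Amend SAP 6.4 as follows.

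1. Assign ET values of PDQ-39, PHQ-9, PGI-C, UPDRS Part 2, UPDRS Part 4 and S&E ADL to the first scheduled visit missed because of withdrawal, as already done for diary and safety data.
2. Say explicitly that this is the only rule for UPDRS Part 4.
3. For CVT-301-004 active rollovers, define the first missed visit in terms of the Section 8 analysis visits. State what happens to ET values that fall at the 004E Month 1 visit or after the 004E Month 9 visit, neither of which feeds the pooled analysis for that group.
4. Keep the ET-to-TV6 assignment as a labelled sensitivity analysis.
5. State whether worst-case imputation applies to PGI-C. If it does, an ET value moved off TV6 counts there as non-improved, and the table should say so.

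The cost is SAP wording and one derivation line; no new data are needed. The downside is fewer TV6 observations for the observed-case scales: at full ET attendance, about 318 to 321 instead of 390. About 28 to 31 of 100 ET values (9% to 10% of TV6 values) would still be labelled TV6, all from withdrawals after TV5.

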## Statistical Analysis Plan

- In case there are PD diary assessments performed during the three days before the ET visit, these assessments will be re-assigned to the first visit at which the PD diary assessments were scheduled but are missing due to the premature withdrawal.
- The safety assessment assessments performed at the ET visit will be re-assigned to the first time point at which the corresponding safety assessments were scheduled but are missing due to the premature withdrawal.
- Any other data collected at the ET visit will not be used.

### 6.5. POOLING OF SITES

Not applicable.

### 6.6. SUBGROUPS

At least the following subgroup analyses have been pre-planned. The subgroup analyses will be performed for selected safety/efficacy endpoints (at least the change from baseline in total daily OFF time). Selected baseline data will be presented for the subgroups as well.

- Patients with baseline PD severity < 2.5 points on the Hoehn & Yahr scale versus patients with baseline PD severity  $\geq$  2.5 points on the Hoehn & Yahr scale
- Patients who are dyskinetic before TV1 versus non-dyskinetic patients. The classification will be done based on the Parkinson's disease diary data. The patients who have recorded at least 1 hour of dyskinesia (either ON with non-troublesome dyskinesia or ON with troublesome dyskinesia) on at least 2 days before TV1 will be classified as dyskinetic
- Patient with the baseline daily levodopa dose less than or equal to the median versus the patients with the baseline daily levodopa dose higher than the median
- Patients who have less than 4.5 hours of PD diary mean daily OFF time before TV1 versus patients who have 4.5 hours or more of OFF time
- Patients with FEV1 <60% of predicted or FEV1/FVC ratio <70% at baseline versus patients with FEV1  $\geq$ 60% of predicted and FEV1/FVC ratio  $\geq$ 70%
- Non-elderly (<65 years) versus elderly ( $\geq$ 65 years) patients
- Female versus male patients

## Statistical Analysis Plan

### 7. DEMOGRAPHIC, OTHER BASELINE CHARACTERISTICS AND MEDICATION

#### 7.1. PATIENT DISPOSITION AND WITHDRAWALS

The patient disposition table will summarize the following and will be presented for each treatment group, as applicable, and overall for APP. In addition, the data will be broken down by treatment/study group (patients who received inhaled CVT-301 in CVT-301-004 study, patients who received placebo in CVT-301-004 study and CVT 301 naïve patients (including CVT-301-005 observational arm patients). The patient disposition table will also be provided for CVT-301-003 and CVT-301-009 roll-over patients. The percentages will be calculated based on the number of patients enrolled to study CVT-301-004E, unless otherwise specified).

- The number of patients screened (i.e. the number of patients in the AAP population)
- The number of patients who failed screening
- The number (%) of patients enrolled into the CVT-301-004E study (% calculated from the AAP population)
- The number (%) of patients in the different study populations (Safety and ITT populations)
- The number (%) of patients who completed the study (based on end-of-study case record page, % calculated from the Safety population)
- The number (%) of patients who withdrew from the study and associated reasons (% calculated from the Safety population)

#### 7.2. DEMOGRAPHIC AND OTHER BASELINE CHARACTERISTICS

Demographics and baseline characteristics will be summarized descriptively for the safety and ITT population by treatment group and overall. In addition, the data will be broken down by treatment/study group. The following variables will be summarized:

- Demographics (age (continuous), age categorized as <65 years versus ≥65 years, gender, ethnicity, race, height, weight, BMI, country)
- Smoking history (current, former, never, Number of Years Smoked and Number of Cigarettes/Day)
- Cognitive status (MMSE)
- Average number of daily OFF episodes experienced from the Screening ON/OFF Log. The screening ON/OFF log data collected on 3 days prior to TV1 will be used

## Statistical Analysis Plan

as baseline. If the data are only available on 1 or 2 days prior to TV1, the available data will be used as baseline. If there is no data prior to TV1, the data collected on 3 days prior to SV2 will be used as baseline.

- Proportion of patients who changed the timing of their usual levodopa medication and proportion of patients who took an extra dose of levodopa or other PD medication from the Screening ON/OFF Log. The screening ON/OFF log data collected on 3 days prior to TV1 will be used as baseline. If the data are only available on 1 or 2 days prior to TV1, the available data will be used as baseline. If there is no data prior to TV1, the data collected on 3 days prior to SV2 will be used as baseline.
- Average daily OFF time, ON time without Dyskinesia, ON time with troublesome and non-troublesome dyskinesia (from PD diary before TV1)
- Proportion of patients with total daily OFF time <4.5 hours or  $\geq 4.5$  hours (from PD diary before TV1)
- Distribution of average daily OFF time in 30-minute intervals (00:00 - 00:30, 00:30 - 01:00 ...). The percentage based on the total daily OFF time will also be presented and is calculated as the average of total OFF time collected three days prior to TV1 and is normalized to 16 awake hours per day.
- PD history (time since diagnosis of PD, duration of levodopa treatment, time since onset of wearing off episodes)
- Total daily levodopa dose, number of levodopa doses per day
- PD disease severity (Modified Hoehn and Yahr Staging in "ON" State)
- UPDRS Part 3 Motor score in ON/OFF (from screening assessment); the change from OFF to ON state in UPDRS part 3 Motor score at the Screening will also be classified as  $\geq 6$  points, or  $\geq 11$  points reduction.
- Baseline Dyskinesia (Dyskinetic before TV1, Non-dyskinetic before TV1). The classification will be done based on the Parkinson's disease diary data. The patients who have recorded at least 1 hour of dyskinesia (either ON with non-troublesome dyskinesia or ON with troublesome dyskinesia) on at least 2 days before TV will be classified as dyskinetic.
- Proportion of patients with FEV1 <60% of predicted or FEV1/FVC ratio <70% at baseline versus FEV1  $\geq 60\%$  of predicted and FEV1/FVC ratio  $\geq 70\%$  (based on the randomization strata).

## Statistical Analysis Plan

- Screening spirometry data: FEV1, FVC, and FEV1/FVC ratio, presented for each motor status, ON or OFF, separately.

Demographics and PD disease data will also be summarized by subgroups (Patients with baseline PD severity < 2.5 points on the Hoehn & Yahr scale versus  $\geq 2.5$  points; Patients who are dyskinetic before TV1 versus non-dyskinetic; Patient with the baseline daily levodopa dose less than or equal to the median versus above median; Patients who have less than 4.5 hours of PD diary mean daily OFF time before TV1 versus 4.5 hours or more; Patients with FEV1 <60% of predicted or FEV1/FVC ratio <70% at baseline versus FEV1  $\geq 60\%$  of predicted and FEV1/FVC ratio  $\geq 70\%$ , Non-elderly (<65 years) versus elderly ( $\geq 65$  years) patients, Female versus Male patients).

### 7.3. MEDICAL HISTORY

Medical history data will be coded using the Medical Dictionary for Regulatory Activities (MedDRA) version 17.0. The medical history data will be summarized with frequencies and percentages of patients with at least one medical history item, and patient frequencies and percentages on the system organ class (SOC) and preferred term (PT) levels. The events will also be summarized. The table will be sorted by overall descending frequency of SOC and then, within a SOC, by overall descending frequency of PT. The medical history will be summarized based on the baseline definition, see [Section 6.2](#).

### 7.4. MEDICATION

All medications will be classified using the Anatomical Therapeutic Chemical (ATC) classification codes and preferred drug names from the World Health Organization Drug Dictionary (WHO-DD), Q1March2014.

For the medications recorded on CRF page “Prior and Concomitant Medications”, medications with a stop date before the first date of study drug dosing will be considered prior medications. Medications with start date or stop date on or after the first date of inhaled CVT-301 dosing will be considered concomitant medications.

Summaries of baseline PD treatment medications (medications which start with ATC code N04) will be presented in tabular form using the ATC Level 4 and preferred term. Other prior medications and concomitant medications will be presented in tabular form using the ATC Level 1, ATC Level 2, and PT. Frequencies and percentages will be presented by treatment group and overall. The counts of medications will also be summarized. The tables will be sorted by overall descending frequency of ATC Level(s) and then, within an ATC Level, by overall descending frequency of PT.

If the medication start date is incomplete, then it will be imputed as follows for the

## Statistical Analysis Plan

purpose of determining concomitance only:

- If the start date is completely missing, the start date will be equal to the first dose date. However, if the stop date is not missing and is before the first dose date, then the stop date will be used instead.
- If the start day is missing, the first day of the month will be used.
- If the start day and month are missing, then the first day of the first month (January) will be used.

If the medication stop date is partial, then it will be imputed as follows for the purpose of determining concomitance only:

- If the stop date is completely missing and the medication is not ongoing, the stop date will be equal to the last dose date or date of completion/withdrawal, whichever is the latest.
- If the stop day is missing, the last day of the month will be used.
- If the stop day and month are missing, then the last day of the last month (December) will be used.

## Statistical Analysis Plan

### 8. EFFICACY

The efficacy evaluation defined below includes data from the patients who were previously enrolled in the CVT-301-004 study and for the CVT 301 naïve patients (including patients from CVT-301-005 observational arm). The data from patients who were enrolled to study CVT-301-003 or CVT-301-009 will not be included in the efficacy summaries and will be listed only.

In general, for the purpose of the efficacy analyses, the visits will be pooled as follows:

Treatment/study group	Study CVT-301-004				Study CVT-301-004E			
	Baseline visit	Week 4 visit	Week 8 visit	Week 12 visit	Baseline visit	Month 1 visit	Month 3-9 visits	Month 12 visit
CVT-301-004, CVT-301 group	Baseline	Month 1	not used	Month 3	not used	not used	Months 6-12	not used
CVT-301-004, placebo group	not used	not used	not used	not used	Baseline	Month 1	Months 3-9	Month 12
CVT-301 naïve patients	NA	NA	NA	NA	Baseline	Month 1	Months 3-9	Month 12
CVT-301-005, Observational, Arm	NA	NA	NA	NA	Baseline	Month 1	Months 3-9	Month 12

